13.1.5. Additional Investigator Responsibilities for SAEs

The safety data recorded in the EDC represent the official record of all AEs and SAEs reported in the study. The Investigator should comply with requests by the Medical Monitor or other Sponsor personnel to record the SAE on the patient's AE eCRF. Other supporting documents such as radiology reports, hospital discharge summaries, and autopsy reports should also be provided, when appropriate. Additionally, upon request by the Sponsor, the Investigator should provide input into the SAE narrative and provide timely information to ensure prompt follow-up and closure of the SAE report.

The Investigator and supporting personnel responsible for patient care should discuss with the Medical Monitor any need for supplemental investigations of SAEs. The results of these additional assessments must be reported to the Medical Monitor.

13.1.6. Notification of Post-Treatment SAEs for Patients Who Continue in the Study

Post-treatment SAEs that occur in patients who remain in the study after investigational product has been discontinued must be reported to the Sponsor within 24 hours by following the instructions provided in [Section 13.1.4.2](#).

SAEs that occur in patients who discontinue investigational product, initiate treatment with commercially available Ocaliva, and remain in the study must be reported to the Sponsor within 24 hours by following the instructions provided in [Section 13.1.4.2](#).

13.1.7. Notification of Post-Study SAEs

All SAEs that occur within 30 days following discontinuation from the study, whether or not they are related to the investigational product, must be reported to the Sponsor within 24 hours by following the instructions provided in [Section 13.1.4.2](#).

If an Investigator becomes aware of an SAE that may be attributable to the investigational product at any time after the end of the study, the Sponsor should be notified immediately (ie, within 24 hours) by following the instructions provided in [Section 13.1.4.2](#).

13.1.8. Follow-Up of AEs and SAEs

All AEs must be followed during the course of the study until the AE resolves, is no longer of clinical concern, has stabilized or is otherwise explained, or the patient is lost to follow-up.

AEs ongoing at the final visit that are deemed to be “possibly, probably, or definitely” related or of other clinical significance must be followed for as long as necessary to adequately evaluate the safety of the patient or until the event stabilizes, resolves, or is no longer of clinical concern. The Investigator must ensure that follow-up includes any supplemental investigations indicated to elucidate the nature and/or causality of the AE. This may include additional laboratory tests or investigations, or consultation with other healthcare professionals, as considered clinically appropriate by the Investigator.

Drug-Induced Liver Injury or Disease Progression

All patients showing possible drug-induced liver injury or disease progression should be followed until all abnormalities return to normal or to the baseline state. Drug-induced liver injury may develop or progress even after the causative drug has been stopped. Results should be recorded in the eCRF. Note that longer follow-up can sometimes reveal an off-drug repetition of what had appeared to be drug-induced liver injury, indicating that liver injury was related to underlying liver disease.

Cholecystitis or Pancreatitis

Patients should be instructed to contact the investigational site if they experience any of the following signs and symptoms: nausea, vomiting, abdominal pain, diarrhea, weight loss, fever and chills, worsening or new fatigue, or weakness. Patients should also be counseled to seek immediate medical assistance if they experience persistent severe abdominal pain.

In the event that cholecystitis and/or pancreatitis is suspected, Investigators should promptly bring patients into the clinic to undergo a complete evaluation, including a physical examination, and laboratory assessments [ie, amylase and lipase]). Investigators should refer to standard of care guidelines on suspected pancreatitis ([Banks 2012](#), [Greenburg 2015](#)). Diagnosis of acute pancreatitis includes 2 of the following:

- Abdominal pain (acute onset of a persistent, severe, epigastric pain often radiating to the back)
- Serum lipase activity (or amylase) at least 3 times greater than the upper limit of normal
- Characteristic findings of acute pancreatitis on computed tomography or magnetic resonance imaging

To ensure appropriate vigilance, amylase and lipase levels should be monitored monthly for 3 months after onset of symptoms, irrespective of whether a diagnosis of cholecystitis and or pancreatitis is confirmed. The Investigator should contact the Medical Monitor upon awareness

of the above (ie, suspected or confirmed diagnosis). Results should be recorded promptly in the eCRF.

13.1.9. Pregnancy and Follow-Up

Pregnancies are not considered AEs in and of themselves; however, if a female study participant becomes pregnant while she is enrolled in the clinical study, she must discontinue treatment with investigational product immediately and the Sponsor must be notified within 24 hours of the Investigator's awareness of the pregnancy by completing the Pregnancy CRF in the EDC system and downloading and completing the Pregnancy Report Form. The Pregnancy Report Form must be emailed to PPD or faxed to PPD. The patient and neonate must be followed for outcome information and/or as considered appropriate by the Investigator and Sponsor.

Completing the Pregnancy Report Form is not a substitute for reporting an AE/SAE when and AE/SAE has occurred. In the situation when an AE/SAE has occurred, the AE/SAE reporting procedures described in [Section 13.1.4](#) must also be followed.

13.2. Other Safety Parameters

13.2.1. Medical History/Demographics

A complete medical history will be obtained from the patient at screening. Demographic characteristics (age, gender, race, and ethnicity) will be recorded.

13.2.2. Medical and Surgical Procedures

Medical and surgical procedures will be recorded at the visits indicated in [Table 1](#).

13.2.3. Physical Examination

To assess for clinical findings, the Investigator or designee will perform a physical examination at the visits specified in the Schedule of Study Procedures (Table 1). A basic physical examination should be performed, including all body systems pertinent to the patient. Smoking and alcohol consumption history and current habits will be recorded. Any clinically significant abnormality should be reported on the AE eCRF page for findings that appear after consent, and on the medical history eCRF for any finding present prior to consent.

13.2.4. Vital Signs and Weight

Vital signs (oral temperature, sitting heart rate, respiratory rate and sitting blood pressure [BP]) and weight will be assessed at indicated visits (Table 1). When taking heart rate, respiratory rate and BP readings, patients should be seated quietly for a minimum of 3 minutes before the readings are taken.

13.2.5. Electrocardiogram

Standard ECGs will be collected at indicated visits (Table 1). The Investigator or designee will review the ECG and findings will be recorded in the eCRF as normal, abnormal but not clinically

significant, or abnormal and clinically significant. Any clinically significant abnormalities on ECGs recorded after Day 1 will also be documented as AEs and entered on the AE page of the eCRF.

Investigative sites must retain a copy of all ECGs evaluated by the Investigator or designee. These ECGs must be clearly labeled with the Patient ID number, date, and time.

13.2.6. Laboratory Assessments

Patients will be instructed to attend each study visit in a fasted state, preferably in the morning, and patients should remain fasted until their blood samples have been collected. At all visits, the Investigator or designee will verify that the patient has fasted for at least 8 hours and record fasting status in the source and eCRF. If the patient reports having eaten (water is permitted) within 8 hours, the Investigator or designee will document accordingly in the source and eCRF and remind the patient that fasting is required before all study visits.

Blood samples for serum chemistry, coagulation, and hematology; and urine samples will be collected at visits as detailed in the Schedule of Study Procedures (see [Table 1](#)). The number and volume of samples to be collected at each visit will be detailed in the laboratory manual.

Full instructions concerning the number and type of samples to be collected at each visit, the required sample volumes, sample collection methods, sample processing, labeling, and shipping will be provided in a separate procedural manual. All necessary collection supplies will be provided by the central laboratory and will be appropriately assembled for the specific evaluations required at each visit.

All patients with laboratory tests containing clinically significant abnormal values are to be followed regularly until the values return to normal ranges; until a valid reason, other than investigational product related AE, is identified; or until further follow-up is deemed medically unnecessary.

Laboratory samples will be stored for a maximum of up to 1 year after the end of the study (depending on stability) in the event that retesting is required, and destroyed after 1 year if not analyzed.

The list of laboratory analytes to be tested is shown in Table 11.

Table 11: List of Laboratory Analytes to be Tested

Laboratory Assessment	Analyte
Serum Chemistry	Albumin, blood urea nitrogen, creatinine, aspartate aminotransferase [AST, SGOT], alanine aminotransferase [ALT, SGPT], ALP, GGT, electrolytes [calcium, chloride, potassium, sodium], glucose, total protein, and blood lipids (total cholesterol, LDL, HDL and VLDL fractions and TG), CPK, magnesium, phosphorus, bicarbonate, unconjugated (indirect) bilirubin, conjugated (direct) bilirubin, total bilirubin, free fatty acids, TFT (TSH, free T3 and free T4)
Hematology	Hemoglobin, hematocrit, white blood count with differential, neutrophils, lymphocytes, monocytes, eosinophils, basophils, platelets, red blood cell count (including MCV, MCH, MCHC)

Table 11: List of Laboratory Analytes to be Tested (Continued)

Laboratory Assessment	Analyte
Coagulation	PT, PTT, INR
Urinalysis; Pregnancy	pH, specific gravity, total protein, glucose, ketones, bilirubin, blood, microscopic exam, urobilinogen, leucocytes, nitrates; albumin, creatinine, albumin/creatinine ratio (if positive); β -hCG
Markers of Cholecystitis and Pancreatitis	Amylase and lipase
Noninvasive measurements of liver fibrosis	ELF (HA, P3NP, and TIMP-1)
PK assessments	OCA (parent and conjugates [glyco and tauro], metabolite OCA-glucuronide)
PD markers	C4, FGF-19 and plasma bile acids

ALP = alkaline phosphatase; ALT = alanine aminotransferase; AST = aspartate aminotransferase; β -hCG = human chorionic gonadotropin; C4 = 7α -hydroxy-4-cholesten-3-one; CPK = creatine phosphokinase; ELF = enhanced liver fibrosis; FGF-19 = fibroblast growth factor-19; GGT = gamma-glutamyl transferase; HA = hyaluronic acid; HDL = high density lipoprotein; INR = international normalized ratio; LDL = low-density lipoprotein; MCH = mean corpuscular hemoglobin; MCHC = mean corpuscular hemoglobin concentration; MCV = mean corpuscular volume; OCA = obeticholic acid; P3NP = procollagen 3 N-terminal peptide; PT = Prothrombin time; PTT = partial thromboplastin time; SGOT = Serum glutamic oxaloacetic transaminase; SGPT = serum glutamic-pyruvic transaminase; T3 = triiodothyronine; T4 = thyroxine; TG = triglyceride; TFT = thyroid function test; TIMP-1 = tissue inhibitor of metalloproteinase 1; TSH = thyroid stimulating hormone; VLDL = very low-density lipoprotein

Laboratory reference ranges for the study will be based on the laboratory vendor range.

Urine based β -hCG pregnancy tests will be performed in female patients of childbearing potential per protocol specified visits (see [Table 1](#)). If a urine pregnancy test is positive, a serum pregnancy test must be performed to confirm the result. If positive, the Sponsor must be notified and the patient will be followed as outlined in [Section 13.1.9](#) until pregnancy outcome.

INR will be calculated based on prothrombin time value by the central laboratory. MELD scores will be calculated based on creatinine, bilirubin, and INR values, with modification by United Network for Organ Sharing. Total OCA will be calculated based on the sum of OCA, glycol-OCA, and tauro-OCA concentrations. Laboratory analyte results may be used to calculate various cardiovascular risk and fibrosis measurement scores.

13.2.7. Patient-Reported Outcomes and Healthcare Resource Use

Data will be collected to determine the effects of OCA on health-related quality of life. Healthcare resource use as well as a general health status assessment (for the purposes of generating health utilities) will be used to support subsequent cost-effectiveness analyses that are relevant to major health care systems around the world. Assessments of patient-reported outcomes will take place during the visits indicated in [Table 1](#).

The following patient-reported outcomes will be used to evaluate the effects of OCA compared to placebo on improvements in health-related quality of life:

- PBC-40: The PBC-40 is a validated disease-specific 40-question quality of life questionnaire, which consists of 6 domains: General Symptoms, Itch, Fatigue, Cognitive Function, Social, and Emotional ([Jacoby 2005](#)).

- EQ-5D-5L: The EQ-5D-5L consists of 2 sections – the descriptive system and the visual analogue scales (VASs). The descriptive system is organized into 5 dimensions: mobility, self-care, usual activities, pain/discomfort, and anxiety/depression. Each dimension has 5 levels: no problems, slight problems, moderate problems, severe problems, and extreme problems. The VAS records the patient’s self-rated health on a 20-cm vertical, line with endpoints labelled “the best health you can imagine” and “the worst health you can imagine” (Herdman 2011, Oemar 2013).
- Pruritus VAS: A VAS will also be used to assess pruritus in individual patients.
- Chronic Liver Disease Questionnaire: The CLDQ is a disease-specific health related quality of life questionnaire for patients with chronic liver disease. The questionnaire includes 29 items in the following domains: fatigue, activity, emotional function, abdominal symptoms, systemic symptoms, and worry). Each question is answered on a scale from 1 (always) to 7 (never) with a higher score corresponding to a better quality of life. The CLDQ produces a summary score and domain scores that correlate with the severity of liver disease (Younossi 1999).

Patients will be asked to complete the questionnaires and initial and date each document. The questionnaires should be filed in the patient’s study records. These may require transcription to the eCRF by study site staff.

Healthcare resource use will be collected from eCRFs including number, reason for and duration of hospitalizations and emergency room visits, number of outpatient physician visits (patient reported), and use of concomitant medications. The purpose is to evaluate the effects of OCA compared to placebo on patient-reported outcomes and healthcare resource.

14. EFFICACY ASSESSMENTS

14.1. Biochemical Measures of Disease Severity

14.1.1. Child-Pugh Score

Child-Pugh Score (Pugh 1973, Lucey 1997) is calculated and reported within the EDC system based on data entered into the eCRF by adding the scores from the 5 factors outlined in Table 12 and can range from 5-15. A total score of 5-6 is considered Grade A (mild, well-compensated disease); 7-9 is Grade B (moderate, significant functional compromise); and 10 and above is Grade C (severe, decompensated disease). Calculation of the CP Score includes Investigator assessments of ascites and hepatic encephalopathy, which may be assessed during the adverse event review at the scheduled visits, as well as total bilirubin, serum albumin, and prothrombin time, which will populate from the central laboratory.

Table 12: Child-Pugh Scoring System

Factor	Units	Points		
		1	2	3
Serum bilirubin	µmol/L	<34	34-50	>50
	mg/dL	<2.0	2.0-3.0	>3.0
Serum albumin	g/L	>35	28-35	<28
	g/dL	>3.5	2.8-3.5	<2.8
Prothrombin time	Seconds prolonged	0-3	4-6	>6
	INR	<1.7	1.7-2.3	>2.3
Ascites		None	Mild	Moderate-Severe
Hepatic encephalopathy ^a		0	Grade 1 or 2	Grade 3 or 4

^a Grade 0: normal consciousness, personality, neurological examination, electroencephalogram
Grade 1: restless, sleep disturbed, irritable/agitated, tremor, impaired handwriting, 5 cps waves
Grade 2: lethargic, time-disoriented, inappropriate, asterixis, ataxia, slow triphasic waves
Grade 3: somnolent, stuporous, place-disoriented, hyperactive reflexes, rigidity, slower waves
Grade 4: unrousable coma, no personality/behavior, decerebrate, slow 2-3 cps delta activity
(Pugh 1973, Lucey 1997), Vilstrup 2014

14.1.2. Model of End Stage Liver Disease Score

The MELD scoring system is used to assess the severity of chronic liver disease. The MELD score is useful in assessing patients with significant decompensation, and the MELD score is now used by the United Network for Organ Sharing in the US and Eurotransplants to manage the organ allocation for liver transplantation. The threshold for placement on an organ transplantation queue varies between regions across the globe.

An increasing MELD score is associated with increased severity of hepatic dysfunction and increased 3-month mortality risk. The MELD score is derived from the patient's serum total bilirubin, serum creatinine, and INR, as appropriate, to predict survival (Kamath 2007). MELD score will be calculated and reported for visits where these parameters are measured (see Table 1).

14.1.3. Changes in Liver Biochemistry and Hepatobiliary Damage

ALP, ALT, AST, GGT, total and direct bilirubin, INR, creatinine, albumin, platelets will be measured according to the frequency listed in Table 1.

14.2. Additional Assessments

14.2.1. Noninvasive Measurements of Liver Stiffness and Fibrosis

The ELF test assesses: HA, P3NP, and TIMP-1. Samples will be assessed in patients according to the schedules presented in Table 1.

The Fibroscan[®] TE device (Echosens, Paris, France) will be used at all study sites that have the equipment to collect hepatic stiffness measurements. These study sites must have the staff trained in the use and data interpretation of the device. This is a validated and non-invasive radiological technique used to assess hepatic fibrosis which will be conducted according to the schedule presented in [Table 1](#).

14.2.2. Markers of FXR activation

Blood samples will be collected in all patients to measure C4, FGF-19, and bile acids. The results of these analyses will be used to assess the PK/PD response of OCA. Blood samples will be assessed in patients according to the schedule presented in [Table 1](#).

14.2.3. Clinical Outcome Events

Clinical outcome events will be evaluated by an Adjudication Committee (described in [Section 15.9](#)) to confirm if they meet the criteria to be considered Clinical Outcome Events.

15. STATISTICAL METHODS AND ANALYSES

Individual patient data obtained from electronic case report forms (eCRFs), central laboratories, external sources, and any derived data will be presented in data listings by patient. All data listings that contain an evaluation date will contain a relative study day. Pre-treatment and on treatment study days are numbered relative to the day of the first dose of investigational product which is designated as Day 1.

All output will be incorporated into Microsoft Word rich text format (.rtf) files, sorted and labeled according to the International Conference on Harmonisation (ICH) recommendations, and formatted to the appropriate page size(s).

Tabulations will be produced for appropriate demographic, Baseline, efficacy, and safety parameters.

For categorical variables, summary tabulations of the number and percentage of patients within each category (with a category for missing data) of the parameter will be presented. Percentage calculations will be based on non-missing data, unless otherwise specified. Percentages are rounded to 1 decimal place, unless otherwise specified.

For continuous variables, the number of patients, mean, standard deviation (SD), standard error of the mean (SEM), median, minimum, and maximum values will be presented. The precision of summary statistics, unless otherwise specified will be as follows: mean and median to 1 more decimal place than the raw data, and SD and SEM to 2 decimal places more than the raw data. In general, the decimal places should not exceed 3 decimal places unless appropriate. Confidence intervals (CIs) will be provided and will be rounded to 1 decimal place, unless otherwise specified.

Time-to-event data will be summarized using Kaplan-Meier (KM) methodology using 25th, 50th (median), and 75th percentiles with associated 2-sided 95% CIs, as well as percentage of censored observations.

There will be no formal hypothesis testing in this study. However, summary statistics for each treatment group will be presented, as well as 95% CIs for the difference between the treatment groups.

15.1. Analysis Populations

The following patient populations will be evaluated and used for presentation and analysis of the data:

- The Intent-to-Treat (ITT) Population will include all randomized patients who receive any amount of investigational product (OCA or placebo). The ITT Population will be the primary population used for summarizing efficacy assessments.
- The Safety Population will include all patients who received at least one dose of investigational product (placebo or OCA). The Safety Population will be the primary population used for safety analyses.
- The PK population will include all patients receiving OCA who have adequate concentration-time profiles to characterize OCA and its conjugates and must not have any major protocol deviations that potentially affect exposure levels.

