12.1. Pharmacokinetic Blood Sampling

Serial and fasting PK assessments will be performed in all patients participating in the study.

[figure not shown]
At Day 1, and Weeks 6, 12, 18, 24, 30, 36, and 48, patients will provide fasted blood samples for measurement of OCA and its conjugates, glyco-OCA and tauro-OCA, and metabolite OCA glucuronide 30 minutes before administration of investigational product (Table 8). Patients will then receive a dose of investigational product with approximately 240 mL of water.

Week 6 Visit should occur 3, 4, or 5 days **after** the Week 6 dose (eg, if the Week 6 dose of investigational product is taken on a Sunday, the patient should come in for the Week 6 Visit between Wednesday and Friday [Figure 3]).

During the treatment period:

- Pharmacokinetic fasting samples will be obtained from all patients at Day 1, and Weeks 6, 12, 18, 24, 30, 36, and 48 prior to dose administration in accordance with Figure 4.
- Serial PK assessments will be performed in all patients at Weeks 12, 18, 24, 30, and 48.

[figure not shown]
Figure 3: Week 6 Sampling Schedule

Week 6 Visit should be scheduled 3 to 5 days after the Week 6 OCA dose for collection of a single steady-state fasting PK sample

IP = investigational product; PK = pharmacokinetic

At Weeks 12, 18, 24, 30, and 48, serial PK blood samples will be obtained at 0.5, 0.75, 1, 1.5, 2, 2.5, 3, 4, 5, 6, 7, 8, 9, and 24 hours postdose (Figure 4) for all patients. The patient will be given the option to return to the clinic the following morning for the 24-hour postdose sample or samples can be obtained by a home health care designee. The home health care agency must be advised one week in advance of the appointment.

Figure 4: Pharmacokinetic Sampling Schedule

At meal timepoints, meals are consumed immediately after the collection of the PK sample

h = hour; IP = investigational product; PK = pharmacokinetic

Patients should not drink additional water for 1 hour after taking the dose of investigational product and will remain fasted until after the 1-hour sample is collected. A meal replacement drink will be provided following collection of the 1-, 4-, and 7-hour PK sample. The nutritional information of the meal replacement drink should be submitted to and approved by the Sponsor in advance. No other food or drink (water is permitted) will be allowed until after the 9-hour sample collection.

Table 8: Acceptable Windows for Pharmacokinetic Sample Collection

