15.2. Determination of Sample Size

To reasonably characterize the PK of OCA in patients with hepatic impairment, a simulation-based approach estimated a requirement of approximately 20 patients in the OCA treatment group assuming a 15% discontinuation rate. A total of 30 patients is adequate with 10 patients on placebo to be included as a comparator and 20 patients on OCA. An additional 20 patients will be enrolled to support safety and efficacy evaluations. Therefore, approximately 50 patients (including at least 20% of patients with CP-C) will be randomized in a 1:1 ratio to 1 of the 2 treatment groups: Placebo and OCA.

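### The PK Population excludes whole patients for a major exposure-affecting deviation, although each OCA patient has five serial profiles and a deviation at one visit need not spoil the others

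*Protocol*

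**What the plan says.** Protocol Section 15.1 defines the PK Population as "all patients receiving OCA who have adequate concentration-time profiles to characterize OCA and its conjugates", and adds that they "must not have any major protocol deviations that potentially affect exposure levels". The Synopsis repeats the definition. Neither place limits the deviation clause to a visit, a profile or a period.

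Section 15.3 bases the PK analysis on this population, using non-compartmental methods. Section 12 draws the combined PK/PD set from it: members with at least one PD assessment after dosing.

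On sampling, Section 12.1 states: "Serial PK assessments will be performed in all patients at Weeks 12, 18, 24, 30, and 48". Under Table 2 these five profiles may fall under up to three dosing regimens.

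On numbers, Section 15.2 reports that a simulation "estimated a requirement of approximately 20 patients in the OCA treatment group assuming a 15% discontinuation rate". It then says: "An additional 20 patients will be enrolled to support safety and efficacy evaluations". The total is about 50 patients randomised 1:1.

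**The concern.** The unit of exclusion does not match the unit of data. Each serial profile is a separate dosing occasion with its own predose sample, in-clinic dose, controlled meals and 24-hour follow-up, and it yields its own non-compartmental parameters. A wrong dose taken around Week 48, for example, says nothing against the profile collected at Week 12. If it is graded major, however, Section 15.1 removes the patient, and up to four sound profiles go with the affected one.

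PK in moderate and severe hepatic impairment is a primary objective, and Section 5.4.1 describes the existing clinical data in these patients as limited. Losing valid profiles from about 25 OCA patients would widen the uncertainty of the estimates the trial was set up to provide. The PK/PD analysis inherits the same loss.

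**Working it through.** **Inputs from the protocol**
- OCA patients required for PK: about 20, at 15% discontinuation (Section 15.2).
- Planned OCA arm: 50 / 2 = 25 (Section 15.2, 1:1 allocation).
- Serial profiles per patient: 5 (Section 12.1).

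**Input that is assumed**
- p, the chance that a serial visit carries a major deviation affecting exposure. No document gives a rate, so p is set at 2%, 5% and 10%, independently across visits.

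**The plan's own figure.** 20 × (1 − 0.15) = 17, and 17 / 0.85 = 20, so the dropout arithmetic reproduces. The simulation behind the 20 cannot be checked, because its variability and precision target are not in the current text.

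**Expected patients before PK exclusions.** 25 × 0.85 = 21.25.

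**Share of profiles kept.** Under the patient-level rule a profile survives only if all five visits are clean, so the share is (1 − p)^5. Under a profile-level rule it is 1 − p. The expected number of patients kept under the patient-level rule is 21.25 × (1 − p)^5. The chance of fewer than 17 is binomial with n = 25 and retention 0.85 × (1 − p)^5.

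| p per visit | Profiles kept, patient-level | Profiles kept, profile-level | Patients kept, patient-level | P(fewer than 17) |
|---|---|---|---|---|
| 2% | 90% | 98% | 19.2 | 0.10 |
| 5% | 77% | 95% | 16.4 | 0.50 |
| 10% | 59% | 90% | 12.5 | 0.94 |

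With no PK exclusions at all, P(fewer than 17) is 0.008.

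**Break-even.** The expected number reaches 17 when (1 − p)^5 = 17 / 21.25 = 0.80, so p = 1 − 0.80^(1/5) = 4.4% per visit. That corresponds to excluding 20% of the patients who remain after discontinuation.

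**Comparison at the visit.** If only affected profiles are dropped, the expected number of patients contributing at each visit is 21.25 × (1 − p): 20.8, 20.2 and 19.1 at 2%, 5% and 10%. All stay above 17.

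**The case against.** **The SAP may deal with this.** Section 15.3 leaves full details of the analyses, methods and outputs to the SAP, which is not at hand, and profile-level handling is often set there. But population membership is not among the things deferred: Section 15.1 states it outright. A SAP that kept a patient after a qualifying deviation would depart from the protocol's definition.

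**Few events may trigger the rule.** A deviation must be both major and relevant to exposure, and the protocol text shown does not define major. For an unfasted patient, Sections 9.7.9 to 9.7.11 only ask the site to record the fact and remind the patient. Noncompliance under Section 9.3 leads to discussion and notification of the Sponsor. Permitted interruptions and dose reductions are not deviations. This objection stands: the frequency of qualifying deviations is unknown and could be low.

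**The model is pessimistic about patient numbers.** Deviations that cluster within patients would remove fewer patients at the same rate per visit. A patient who stops after Week 12 may already have an adequate profile, yet is counted as lost. Both points stand.

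**Two stronger readings are not supported.** A reader might infer that the rule is likely to leave the PK set too small. But 17 is back-calculated and is not a stated requirement, the study has no formal hypothesis testing, and the 25-patient arm leaves about four patients of slack. A reader might also infer that the sickest patients would be lost preferentially. That is conceivable, but nothing in the protocol relates deviation frequency to disease severity.

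**Conclusion.** The point holds as a badly fixed rule on the unit of exclusion. Read as written, Section 15.1 discards profiles that nothing has compromised, in a primary-objective analysis and in the PK/PD analysis that depends on it.

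Its size depends on an assumed deviation rate. Under independence, the avoidable loss is about 8 percentage points of profiles at 2% per visit (98% against 90%), 18 at 5% (95% against 77%) and 31 at 10% (90% against 59%). The loss arises at any nonzero rate and does not depend on crossing 17 patients. A shortfall against 17 in expectation needs more than about 4.4% of serial visits to carry a major, exposure-affecting deviation, and missing 17 would breach no criterion in the protocol.

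This is a change worth making because the better rule costs little. It does not show that the trial's PK objective is in jeopardy.

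**What to change.** In Section 15.1 and the Synopsis, define the PK Population as all patients who received OCA and have at least one evaluable concentration-time profile. Move the deviation criterion to the profile: exclude only the profile or profiles affected by a major deviation that potentially affects exposure. Make these decisions before unblinding and list each excluded profile with its reason. The combined PK/PD set in Section 12 then follows without further change.

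The review must also consider carry-over, that is, whether a deviation at or before one visit could still affect a later profile; if so, that profile is flagged too.

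The cost is a sentence in two places, a per-profile flag in the PK dataset, and a blinded review of each profile instead of each patient. No extra patients, visits or samples are needed.
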